We also conducted *in vitro* studies of AT-101 and observed its ability to induce apoptosis in B-CLL cells. Thus, AT-101 is a novel, oral agent with ability to target Bcl-2 family of antiapoptotic protein that has demonstrated *in vitro* and in patient anti-CLL activity. Collectively the pre-clinical and clinical data available and presented here and the data available on Lenalidomide allow us to put forward the following hypothesis: **Hypothesis:** Concurrent targeting of B-CLL cell microenvironment by lenalidomide and the tumor cell itself by AT-101 will result in an enhanced antileukemic effect (**Fig 4**). Therefore we propose to conduct a phase I/II clinical trial to first determine the maximum

tolerated dose of fixed dose of AT-101 in combination with escalating doses of Lenalidomide and subsequently investigate the clinical efficacy of this combination.

Rationale for the combination and dosing:

Developing a novel regimen for relapsed /refractory B-CLL patients is an unmet need. AT-101 and lenalidomide have been tested in phase II studies independently and have

demonstrated anti-leukemic potential. Despite encouraging results most patients only achieved partial remission with single agent use of these agents. There are several important reasons that rationalize to develop the combination of lenalidomide with AT-101 these are; (1) both have clinically active in patients with B-CLL (2) They have non overlapping toxicities (major toxicity for lenalidomide is hematologic while that for AT-101 is gastrointestinal) (3) both an be delivered orally and are patient convenient (4) Both have mutually exclusive targets (lenalidomide targets the microenvironment and results in immune activation while AT-101 down regulates the prosurvival signals of Bcl-2 family of proteins i.e., Bcl-2, Mcl-1 resulting in enhanced susceptibility to undergo apoptosis).

We will initiate lenalidomide at 5mg per day, while using the sample 21 out of 28 day cycle schedule as published previously. This is the minimum dose at we were able to demonstrate antileukemic effects of lenalidomide. The dose of lenalidomide will be escalated over 4 cohorts as outlined later in the study protocol. Although the administered dose in our previous study was 25mg / day the most tolerable dose (in terms of hematologic) was 20mg / day. Therefore in this study we propose that the maximum dose to be investigated in combination with AT-101 be 20mg/day.

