8.2 Lenalidomide

A new course of treatment may begin on the scheduled Day 1 of a new cycle if:

- The ANC is $\geq 1,000/\mu$ L;
- The platelet count is $\geq 25,000/\mu$ L;
- Any lenalidomide-related allergic reaction/hypersensitivity or sinus bradycardia/ other cardiac arrhythmia adverse event that may have occurred has resolved to ≤ grade 1 severity;
- Any other lenalidomide-related adverse event that may have occurred has resolved to \leq grade 2 severity.

If these conditions are not met on Day 1 of a new cycle, the subject will be evaluated weekly and a new cycle of lenalidomide will not be initiated until the toxicity has resolved as described above. If lenalidomide dosing was omitted during the previous cycle and was restarted with a one-level dose reduction without requiring an interruption for the remainder of the cycle, then that reduced dose level will be initiated on Day 1 of the new cycle. If lenalidomide dosing was omitted for the remainder of the previous cycle or if the new cycle is delayed due to toxicity newly encountered on the scheduled Day 1, then the new cycle will be started with a one-level dose reduction.

If either drug is discontinued, patient will come off treatment and go to event monitoring.

| → → Use the NCI Common Terminology Criteria for Adverse Events (CTCAE) version 4.0 unless otherwise specified $\leftarrow \leftarrow$ | | | | |
|---|---|--------------|---|--|
| CTCAE System/Organ/Class (SOC) | ADVERSE EVENT | AGENT | ACTION | |
| | BASED ON INTERVAL | ADVERSE E | EVENTS (Days 2-28) | |
| Investigations | Platelet count decreased*: (Platelets < 10,000/mm ³) | | Omit dose. Follow CBC weekly. If thrombocytopenia resolves to ≤ grade 3 restart lenalidomide at the same dose level. | |
| | | | If thrombocytopenia < 10,000/mm³ recurs, reduce dose by one dose level (5 mg) and continue therapy when platelet count ≥ 25,000/mm³. | |
| | Grade 4 Neutrophil count | | • Omit dose. | |
| | decreased* | | • Follow CBC weekly. | |
| | | Lenalidomide | If neutropenia has resolved to ≤ grade 2, resume dose at same level with GCSF support. | |
| Blood and lymphatic | ≥ Grade 3 Febrile | omi | Omit dose. | |
| system disorders | neutropenia | de | • Follow CBC weekly. | |
| | | | If neutropenia has resolved to ≤ grade 2, resume dose at same level with GCSF support. | |

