8.3 AT-101

During the study period it is the goal to prescribe the fully intended dose of AT-101. It is expected that toxicity of AT-101 can be solved with appropriate measures. However, in case of severe toxicity (grade \geq 3) attributed (possibly, probably or definitively) to AT-101, treatment will be held for a maximum of 8 weeks. If toxicities resolve to \leq grade 1, patients may resume treatment. Patients who are resumed on treatment will be started at a lower dose of AT-101 (25% dose reduction or 30mg BID); if the toxicity recurs (grade \geq 3) then one more dose reduction (50% dose reduction or 20mg BID) will be allowed (upon resolution of toxicity \leq grade 2). If toxicity recurs \geq grade 3, patients will be removed from the study treatment and go to event monitoring.

Note: No dose reduction is allowed in cycle #2 as this is the MTD defining cycle.

| \rightarrow \rightarrow Use the NCI Common Terminology Criteria for Adverse Events (CTCAE) version 4.0 unless | | | | | | | |
|---|--|-----------|--|--|--|--|--|
| otherwise specified $\leftarrow \leftarrow$ | | | | | | | |
| CTCAE System/Organ/Class (SOC) | ADVERSE EVENT | AGENT | ACTION | | | | |
| BASED ON INTERVAL ADVERSE EVENTS (Days 2-3) | | | | | | | |
| Gastrointestinal disorders | BASED ON INTERVAL ≥ Grade 2 Nausea ≥ Grade 2 Vomiting Any Grade Abdominal pain | ADVERSE E | For any of these events that last longer than 48 hours, AT-101 should be omitted and the following actions are recommended: Physical examination, including assessment of vital signs Screening abdominal radiography to include an abdominal series to exclude ileus, small bowel obstruction (SBO), or pneumatosis intestinalis. Consideration for obtaining a CT scan with contrast of the abdomen should be made based on clinical judgment If ileus, non-mechanical SBO, or pneumatosis intestinalis are excluded, AT-101 dosing may be reinstated. If a patient is determined to have ileus, SBO, or pneumatosis intestinalis, AT- | | | | |
| | | | 101 dosing should be permanently discontinued and expectant management with supportive care is recommended, unless clinical signs or symptoms are present that suggest | | | | |
| | | | septicemia or abdominal catastrophe that warrants surgical management. | | | | |

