16.5 Data & Safety Monitoring

- 16.51 The principle investigator(s) and the study statistician will review the study at least twice a year to identify accrual, adverse event, and any endpoint problems that might be developing. The Mayo Clinic Cancer Center (MCCC) Data Safety Monitoring Board (DSMB) is responsible for reviewing accrual and safety data for this trial at least twice_a year, based on reports provided by the MCCC Statistical Office.
- 16.52 Adverse Event Stopping Rule for phase II patients: The stopping rule specified below is based on the knowledge available at study development. We note that the rule may be adjusted in the event of either (1) the study re-opening to accrual or (2) at any time during the conduct of the trial and in consideration of newly acquired information regarding the adverse event profile of the treatments under investigation. The study team may choose to suspend accrual because of unexpected adverse event profiles that have not crossed the specified rule below.

Accrual will be temporarily suspended to this study if at any time we observe events considered at least possibly related to study treatment (i.e. an adverse event with attribute specified as "possible," "probable," or "definite") that satisfy either of the following:

- if 5 or more patients in the first 14 treated patients experience a grade 4 or higher non-hematologic adverse event at least possibly related to treatment.
- if after the first 14 patients have been treated, 30% of all patients experience a grade 4 or higher non-hematologic adverse event at least possibly related to treatment.

We note that we will review grade 4 and 5 adverse events deemed "unrelated" or "unlikely to be related", to verify their attribution and to monitor the emergence of a previously unrecognized treatment-related adverse events

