Appendix V Grading Scale for Hematologic Toxicity in CLL Studies

Non Hematologic Toxicity will be scored using NCI CTCAE (version 4.0) for toxicity and adverse event reporting.

Hematologic toxicity will be assessed using IWCLL/Hallek December 2008

Grading scale for hematologic toxicity in CLL studies

| Grade [*] | Decrease in platelets ¹ or Hb ⁺ (nadir) from pretreatment value, % | Absolute neutrophil count/µL ³ (nadir) |
|--------------------|--|--|
| 0 | No change to 10% | ≥ 2000 |
| 1 | 11%-24% | \geq 1500 and < 2000 |
| 2 | 25%-49% | $\geq 1000 \text{ and} < 1500$ |
| 3 | 50%-74% | \geq 500 and < 1000 |
| 4 | $\geq 75\%$ | < 500 |

^{*} Grades: 1, mild; 2, moderate; 3, severe; 4, life-threatening; 5, fatal. Death occurring as a result of toxicity at any level of decrease from pretreatment will be recorded as grade 5.

[†]Platelet counts must be below normal levels for grades 1 to 4. If, at any level of decrease, the platelet count is $< 20 \times 10^{9}/L$ (20 000/µL), this will be considered grade 4 toxicity, unless a severe or life-threatening decrease in the initial platelet count (eg, $20 \times 10^{9}/L$ [20 000/µL]) was present pretreatment, in which case the patient is not evaluable for toxicity referable to platelet counts.

[‡]Hb levels must be below normal levels for grades 1 to 4. Baseline and subsequent Hb determinations must be performed before any given transfusions. The use of erythropoietin is irrelevant for the grading of toxicity but should be documented.

[§]If the absolute neutrophil count (ANC) reaches $< 1 \ge 10^{9}$ /L (1000/µL), it should be judged to be grade 3 toxicity. Other decreases in the white blood cell count, or in circulating neutrophils, are not to be considered because a decrease in the white blood cell count is a desired therapeutic endpoint. A gradual decrease in granulocytes is not a reliable index in CLL for stepwise grading of toxicity. If the ANC was $< 1 \ge 10^{9}$ /L (1000/µL) before therapy, the patient is not evaluable for toxicity referable to the ANC. The use of growth factors such as G-CSF is not relevant to the grading of toxicity, but should be documented.

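### No related death by itself triggers the numeric phase II suspension rule in Section 16.52, and a related death recorded under a hematologic term is not counted at all

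*Combined protocol and SAP*

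**What the plan says.** Section 16.52 opens its rule with "Accrual will be temporarily suspended to this study if at any time we observe events considered at least possibly related to study treatment" and then gives two limits. Under that same attribution requirement, the first is crossed when "5 or more patients in the first 14 treated patients experience a grade 4 or higher non-hematologic adverse event". The second applies once 14 patients have been treated, and is crossed when "30% of all patients experience a grade 4 or higher non-hematologic adverse event at least possibly related to treatment". Neither limit has a hematologic component or a separate provision for grade 5.

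Appendix V, the hematologic grading scale, adds: "Death occurring as a result of toxicity at any level of decrease from pretreatment will be recorded as grade 5". Section 10.52 asks for each death to be attributed to a CTCAE term where possible, but no section says how a death following cytopenia is to be classified for the 16.52 count.

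Other provisions also bear on deaths:

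- Section 10.52 requires 24-hour reporting of any death within 30 days of the last dose, and of later deaths at least possibly related.
- Section 16.33 lets adverse events inform a decision to terminate.
- Section 16.51 has the DSMB review safety at least twice a year.
- Section 16.52 allows the rule to be adjusted, and allows the team to suspend accrual for unexpected adverse event profiles that have not crossed it.

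**The concern.** A numeric suspension rule fixes in advance what will make the trial pause, so that the pause does not depend on judgement at the time. This rule leaves the gravest outcome to judgement in two ways.

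First, a related death recorded under a hematologic term is not counted. The background section says that the "major toxicity for lenalidomide is hematologic while that for AT-101 is gastrointestinal", and Section 15.17 lists neutropenia and thrombocytopenia in the boxed warnings, so such a death is foreseeable. If the same death were recorded as sepsis or haemorrhage, it would count. The rule's response then turns on a coding choice that the plan does not specify.

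Second, a related non-hematologic death is pooled with grade 4 events at limits of 5 in 14 and 30%. Those limits may be reasonable for grade 4 toxicity. They are very high if what accumulates is deaths.

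At stake is whether patients continue to be enrolled after one or more related deaths before anyone is obliged to stop and look.

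**Working it through.** The documents give no tolerable toxicity rate and no operating characteristics for this rule, so there is no stated figure to reproduce. The properties below are computed from its wording.

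**Inputs**

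- Limit 1 (16.52): 5 or more patients with a counted event among the first 14.
- Limit 2 (16.52): 30% of all patients after the first 14, read as at least 0.30 × n.
- Maximum evaluable patients in phase II (16.12): 37.
- The rule applies at any time (16.52), so it is checked after every patient.

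**Thresholds.** For n up to 14 the threshold is 5. For n = 15 to 37 it is 0.30 × n rounded up: 5 at n = 15 and 16, 6 at n = 17 to 20, and so on to 12 at n = 37.

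**Largest number of deaths by patient 14 without a trigger.** This is 5 − 1 = 4, and 4/14 = 29%.

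**Probability of suspension.** Let p be the true rate of counted events, here related non-hematologic deaths with no other counted event.

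- By patient 14: P = 1 − Σ(k = 0 to 4) C(14,k) p^k (1−p)^(14−k). At p = 0.10 this is 0.0092.
- By patient 37: an exact patient-by-patient binomial recursion. After each patient, the probability mass at or above the threshold is moved to the suspended state and the rest carried forward.
- At least one such death in 37 patients: 1 − (1−p)^37.

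| True rate p | Suspended by 14 | Suspended by 37 | At least one death in 37 |
|---|---|---|---|
| 5% | 0.0004 | 0.001 | 0.85 |
| 10% | 0.009 | 0.022 | 0.98 |
| 20% | 0.130 | 0.289 | >0.99 |
| 30% | 0.416 | 0.742 | >0.99 |

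For deaths recorded under a hematologic term, p contributes nothing to the count, so they cannot trigger the rule at any rate.

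**The proposed trigger.** With suspension at the first related death, the probability of at least one pause in 37 patients is 1 − (1−q)^37 for a true related-death rate q. At q = 2% this is 1 − 0.98^37 = 0.53. At 5% and 10% it is 0.85 and 0.98.

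**The case against.** The strongest reply is that the rule is not the only protection. Deaths are reported within 24 hours, and serious events go at once to the sponsor and to both drug companies. The regulatory unit handles IRB reporting, and the need for FDA submission is assessed. Section 16.33 and the adjustment clause in 16.52 allow action at any time, and grade 4 and 5 events called unrelated or unlikely are re-checked. All of this stands, and it would be wrong to say that the plan lets deaths pass unnoticed. But these provisions report, review or permit; none requires a pause. The suspension clause in 16.52 is optional and worded for unexpected profiles, which does not clearly reach toxicities listed as known in Section 15. At the 10 to 15 patients a year in 16.13, 5 to 7.5 more patients could enrol in the six months between DSMB reviews.

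Leaving cytopenias out of the rule is also defensible in CLL. Entry allows platelets down to 30,000/mm³, and Section 10.41 exempts non-hospitalised cytopenias up to grade 4 from expedited reporting. That supports excluding grade 4 hematologic events, but not excluding deaths. Phase I does count hematologic dose-limiting toxicity, but only in cycle 2 (Section 7.22), while treatment may run to 12 cycles.

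Four stronger readings are tempting and are not supported.

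- *That 11 deaths in 37 patients (29.7%) would pass.* The rule binds at every patient. Of all orderings of 11 events among 37 patients, about 93% cross a limit before the end.
- *That a death from cytopenia can never count.* It counts if coded under a non-hematologic term such as sepsis.
- *That the rule misses the main toxicity of both drugs.* Grade 4 and 5 gastrointestinal events are counted.
- *That grade 3 ileus should be added because it ends treatment.* The Section 8.3 table says AT-101 "dosing should be permanently discontinued and expectant management with supportive care is recommended", and Section 8.2 says "If either drug is discontinued, patient will come off treatment and go to event monitoring". The general text of 8.3 instead describes holding and resuming after severe toxicity, and the two should be reconciled. The 5% to 15% ileus rates in 15.27 come from daily dosing. For three-day pulses every 21 days with docetaxel, the background reports about 1 case in 200, or 0.005 × 37 ≈ 0.2 cases here. Adding 0.5 points to a 15% counted rate moves the suspension probability only from 0.109 to 0.123. The background also names obstruction as dose limiting on an every-other-week pulse schedule, so the rate is uncertain, but the case for changing the rule is not made.

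**Conclusion.** The point holds for deaths. The numeric rule does not count related deaths recorded under a hematologic term, and it gives a related non-hematologic death no more weight than a grade 4 event. Four related deaths in the first 14 patients cross no limit. Even a 20% rate of related non-hematologic death would suspend accrual in only 29% of full-length trials if nothing else were counted.

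These probabilities assume independent patients, immediate knowledge of each outcome, 37 patients under the rule, no early stop for futility, and no other counted events. Grade 4 non-hematologic events would raise them. The share of cytopenia-related deaths that would be coded as hematologic is unknown.

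This is a gap in the automatic trigger, not in reporting or oversight, and it does not affect the efficacy design. It is a cheap improvement worth making.

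**What to change.** Add one sentence to 16.52: any grade 5 event at least possibly related to treatment, whether recorded under a hematologic or a non-hematologic term, temporarily suspends accrual pending DSMB review. Leave the limits of 5 in 14 and 30% as they are for grade 4 or higher non-hematologic events. The new sentence also removes the dependence on coding for deaths.

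The cost is short accrual pauses, some of them for deaths that review will judge acceptable. At a true related-death rate of 2%, about 53% of full 37-patient trials would pause at least once. Each pause is temporary and ends with a DSMB decision. The sample size, the response criteria for success and the treatment rules do not change.

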16.6 Inclusion of Women and Minorities

- 16.61 This study will be available to all eligible patients, regardless of race, gender, or ethnic origin.
- 16.62 There is no information currently available regarding differential effects of this regimen in subsets defined by race, gender, or ethnicity, and there is no reason to expect such differences to exist. Therefore, although the planned analysis will, as always, look for differences in treatment effect based on racial and gender groupings, the sample size is not increased in order to provide additional power for subset analyses.
- 16.63 The geographical region served by MCCC has a population which includes approximately 3% minorities. Based on prior MCCC studies involving similar disease sites, we expect about 3-5% of patients will be classified as minorities by race and about 40% of patients will be women. Expected sizes of racial by gender subsets are shown in the following table:

| Accrual Targets | | | | | | |
|---|------------|-------|-------|--|--|--|
| Ethnic Category | Sex/Gender | | | | | |
| Ethnic Category | Females | Males | Total | | | |
| Hispanic or Latino | 0 | 1 | 1 | | | |
| Not Hispanic or Latino | 24 | 35 | 59 | | | |
| Ethnic Category: Total of all subjects | 24 | 36 | 60 | | | |
| Racial Category | | | | | | |
| American Indian or Alaskan Native | 0 | 0 | 0 | | | |
| Asian | 0 | 0 | 0 | | | |
| Black or African American | 1 | 1 | 2 | | | |
| Native Hawaiian or other Pacific Islander | 0 | 0 | 0 | | | |
| White | 23 | 35 | 58 | | | |
| Racial Category: Total of all subjects | 24 | 36 | 60 | | | |

| Ethnic Categories: | Hispanic or Latino – a person of Cuban, Mexican, Puerto Rican, South or Central American, or other Spanish culture or origin, regardless of race. The term "Spanish origin" can also be used in addition to "Hispanic or Latino." Not Hispanic or Latino |
|-----------------------|---|
| Racial Categories: | American Indian or Alaskan Native – a person having origins in any of the original peoples of North, Central, or South America, and who maintains tribal affiliations or community attachment. Asian – a person having origins in any of the original peoples of the Far East, Southeast Asia, or the Indian subcontinent including, for example, Cambodia, China, India, Japan, Korea, Malaysia, Pakistan, the Philippine Islands, Thailand, and Vietnam. (Note: Individuals from the Philippine Islands have been recorded as Pacific Islanders in previous data collection strategies.) Black or African American – a person having origins in any of the black racial groups of Africa. Terms such as "Haitian" or "Negro" can be used in addition to "Black or African American." Native Hawaiian or other Pacific Islander – a person having origins in any of the original peoples of Hawaii, Guam, Samoa, or other Pacific Islands. White – a person having origins in any of the original peoples of Europe, the Middle East, or North Africa. |

17.0 Pathology Considerations/Tissue Biospecimens

17.1 Summary Table of Research Tissue Specimens to be Collected for this Protocol

| Correlative Study (Section for more information) | Mandatory or Optional | Type of Tissue to Collect | Block, Slides, Core, etc. (# of each to submit) | Visit 1:Baseline Visit 2: Within 24 hours of tumor flare Visit 3: 48-72 hours after start of tumor flare Visit 4: 7-10 days after start of tumor flare Visit 5: At resolution of tumor flare | Process at site? (Yes or No) | Temperature Conditions for Storage /Shipping |
|--|--------------------------|--|---|--|---------------------------------------|--|
| Tumor Flare Reaction | Optional | Lymph node aspirate or biopsy | 2-3 cores | Х | Yes | Tissue to be transferred to pathology and parafin embeded block will be prepared |

17.2 Collection and Processing

- 17.21 All samples will be collected and stored at [name] laboratory
- 17.3 Background and Methodology
 - 17.31 Lymph Node Aspirate/biopsy: Lymph node biopsies (on accessible lymph nodes) will be done on all consenting participants at baseline. If patients experience tumor flare reaction, during any cycle, then lymph node biopsy/aspirates (2-3 cores) will be performed during and then after resolution of the TFR. Since the timing of the TFR varies, the treating physician in consultation with [name] will determine the appropriate time for performing the biopsy/aspirate on thelymph node. The site of lymph node biopsy will be determined by the treating physician and /or the study chair. NOTE: Patients with no accessible lymph nodes may not participate in this correlative research, but can still participate in all other correlative research associated with this study.

